13.2 Accrual Rate

Clear cell sarcoma is an ultra-rare sarcoma subtype with a low incidence in the general population. To date, few prospective studies have been conducted that will allow for precise estimation of accrual rate. The CREATE trial, a multi-center

European study, enrolled 43 patients within two years. As this multi-center international study will be restricted to the HLA-A*02:01-positive population, we estimate a longer accrual time than CREATE. We anticipate an accrual rate of 6 - 12 patients per year. and the total accrual rate is estimated to range between two and four years.

13.3 Stratification Factors

Not applicable

13.4 Analysis of Secondary Endpoints

CCS is a rare tumor and approximately one-third of patients are expected to be HLA-A*02:01-positive.³⁵ As a secondary endpoint, we will compare the median PFS of patients treated with tebentafusp to historical controls, and we will leverage the HLA-ineligible CCS population to compare the median PFS of patients treated with physicians' choice of therapy to the HLA-A*02:01-positive population treated with tebentafusp. This secondary endpoint will provide a second point of comparison to historical controls. Prospectively enrolling 24 patients with CCS who are HLA-A*02:01-negative and treated with physicians' choice of therapy will provide 80% power to detect a HR of 2 at a one-sided type I error rate of 0.1 when compared to tebentafusp-treated CCS patients, respectively.

Additional secondary endpoints will be: to estimate the best ORR by RECIST 1.1 and by Choi criteria, to estimate the median duration of response among responders, to estimate the overall CBR and CBR at 12 and 24 weeks, to estimate the PFS at 12 weeks and median PFS, to estimate the median OS, and to further describe the safety as assessed by CTCAE version 5.0.

13.5 Exploratory Analyses

Tumor tissue

The potential effect of tebentafusp on selected biomarker expression measured in pre- and on-treatment tumor tissue will be assessed using the paired t-test for continuous variables and the McNemar test for binary variables. The significance of differences in the frequency of individual cell populations and expression of individual markers between pre- and on-treatment measurements will be evaluated using paired t-tests, and those between responders and non-responders by two-sample t-tests. We will assess the association of immune cell populations and immune suppression markers at each time point, as well as the treatment-induced change in each, by logistic regression for binary outcomes and by Cox regression with time dependent covariates for time to event outcomes. A sample size of n=23 will allow 92% (82%) power to detect a change of 0.7 (0.6) standard deviation in a biomarker expression after treatment.

Peripheral blood ctDNA analysis

The time course of the abundance of the *EWSR1::ATF1* fusion in ctDNA will be investigated numerically using summary statistics and graphically using spaghetti plots

for individual patients and in aggregate. Their trends over time will be categorized either by visual inspection (if there are clear trend groups such as monotonically increasing or monotonically decreasing) or by pattern recognition methods such as K-means clustering. If there are a reasonable number of events for each clinical outcome (such as ORR, CBR, PFS, and OS), we will assess their association with binary outcomes using generalized estimating equations and with time-to-event outcomes using Cox regression with time dependent covariates. The concordance of detected fusion sequences in ctDNA and tissue will be assessed using cross-tabulation and kappa statistics. Given the limited sample size, these analyses are exploratory in nature and for generation of hypotheses.

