Patients who are HLA-A*02:01-negative and ineligible to receive tebentafusp will be prospectively enrolled onto a separate study arm and treated with physicians' choice of treatment. They will also be radiographically assessed at the same schedule as patients treated with tebentafusp, if feasible, and kept on this treatment arm until progression of disease or unacceptable toxicity on the physicians' choice regimen.

Maximum Total Number of Subjects

23 patients will be on treatment arm. 24 patients will be on a physician's choice arm. This equals 47 total.

Target Population

Unresectable or metastatic clear cell sarcoma patients who are HLA-A*02:01 positive.

Anticipated Length of Study (patient enrollment period, overall length including follow-up)

5 years total: 3 years of enrollment, 1 year on treatment, 1 year follow-up

Study Drug (s)

Tebentafusp

Dosing and Administration

Tebentafusp will be administered via IV infusion on Days 1, 8, and 15 of a 21-day cycle. Treatment on C1D1 will be 20mcg, treatment on C1D8 will be 30 mcg. After this initial dosing period, beginning at C1D15 and beyond, patients are eligible to receive the full dose of 68 mcg. This escalated dose administered at C1D15 will be the dose used for the remainder of the treatment period unless dose reduction is implemented for toxicity.

Efficacy Evaluations

Radiographic assessment via CT or MR (where CT is not feasible or per the investigator's discretion) will occur at baseline and every subsequent 6 weeks through 48 weeks, and then every 9 weeks thereafter (+/- 7 days on scan date).

Tumor evaluations for the purposes of the primary endpoint are made based on RECIST v1.1. The efficacy assessments and definitions of best response and PD for the purposes of the primary endpoint of ORR described in this study are based on the RECIST v1.1 (section 11.1.4).

Safety Evaluations/ Concerns

Tebentafusp is FDA-approved for HLA-A*02:01-positive adult patients with unresectable or metastatic uveal melanoma. Patients will be monitored for AEs and toxicities will be reported per CTCAEv5.

Special warnings and precautions listed in the investigator's brochure include:

- 1) Cytokine release syndrome
- 2) Rash
- 3) Elevated liver enzymes

Other clinically relevant AEs include:

- 1) Tumor flare/pain
- 2) Elevated pancreatic enzymes
- 3) Lymphopenia

Correlative Studies

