2.3 Rationale

CCS is Characterized by an EWS-ATF1 Fusion and Expression of Melanocytic Antigens

As Enzinger noted in the 1960s, CCS cells occasionally contain discrete foci of melanin on light microscopy, which can manifest as pigmented lesions on the skin above the tumor.¹⁰ Ultrastructural studies later found melanosomes on electron microscopy,¹¹ raising the possibility that CCS is actually a form of melanoma.¹² In their large case series, Chung and Enzinger found 72% of cases positively stained for intracellular melanin. They concluded that CCS represents a malignant neuroectodermal tumor derived from potentially melanogenic cells arising from the neural crest, and therefore proposed a new name for the disease: malignant melanoma of soft parts.⁴

In support of this theory, CCS were found to stain positive for S-100 on immunohistochemistry (IHC), which was initially found on astrocytes, oligodendrocytes, Schwann cells, and melanocytes, the latter two originating from the neural crest.¹³ In addition, CCS stains positively for other melanoma-specific antibodies, including HMB-45, microphthalmia transcription factor (Mitf), and Melan-A.^{14,15}

In 1991, Bridge et al identified a balanced translocation between chromosomes 12 and 22 in select cases of CCS.¹⁶ The translocation t(12;22)(q13-14;q12) represents a fusion between *EWS* and *ATF1*, which contains the transactivating domain of EWS linked to most of the ATF1 protein, including a bZIP domain that mediates protein dimerization and DNA binding through dimerization with the transcription factor CREB.^{17,18}

To better define the relationship between CCS and other sarcomas, Segal et al at MSKCC performed gene expression analysis to compare CCSs, melanoma, and soft tissue sarcoma. Using both hierarchical clustering and an unsupervised principal components analysis, soft tissue sarcomas clustered together, while CCS clustered with melanoma. A supervised machine-learning algorithm also categorized all CCSs as melanomas. The genes *PMEL17* (encoding gp100), *SOX10*, and *MITF* were most consistently expressed in CCS.¹⁹ Schaefer and colleagues performed a similar analysis on CCS cell lines and other sarcoma subtypes, identifying *PMEL17*, *MITF*, and *SOX10* as the most abundantly expressed genes in CCS compared to other sarcomas.²⁰

Further pre-clinical work found the EWS-ATF1 fusion to constitutively activate the *MITF* promoter, leading to increased *MITF* expression and downstream expression of the

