3. PATIENT SELECTION

3.1 Eligibility Criteria

- 3.1.1 Age \geq 18 years
- 3.1.2 Histologically confirmed diagnosis of HMB-45+ clear cell sarcoma which is unresectable and/or metastatic
- 3.1.3 HLA-A*02:01 positive
- 3.1.4 ECOG Performance Status of \leq 2 at screening
- 3.1.5 At least one site of measurable disease on CT/MRI scan as defined by RECIST v 1.1 criteria. Baseline imaging must be performed within 28 days of Cycle 1 Day 1 of study.
- 3.1.6 Adequate organ function within 28 days of Day 1 of study defined as:
 - Absolute Neutrophil Count (ANC) \geq 1.5
 - Platelets \geq 75
 - ALT and AST \leq 2.5 x institutional upper limit of normal (ULN) or \leq 5.0 x institutional ULN if considered due to tumor
 - Alkaline phosphatase \leq 2.5 x institutional ULN unless considered due to tumor
 - Serum bilirubin \leq 1.5 x institutional ULN. **NOTE:** Patients with elevated bilirubin secondary to Gilbert's disease are eligible to participate in the study

- Serum creatinine $\leq 1.5 \times$ institutional ULN or 24-hour creatinine clearance ≥ 50 ml/min (calculated creatinine clearance using Cockcroft formula is acceptable)
- 3.1.7 Written, voluntary informed consent
- 3.1.8 Patients must demonstrate progression of disease by RECIST 1.1 within 6 months of study enrollment. Newly diagnosed patients with unresectable or metastatic disease and only one baseline scan are eligible to screen and enroll.
- 3.1.9 All other relevant medical conditions must be well-managed and stable, in the opinion of the investigator, for at least 28 days prior to first administration of study drug

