9.2.2 Gene Expression Profiling

Tumor cores will be analyzed by RNA sequencing. Software tools will be utilized to generate and perform quality control on BAM files and to quantify gene expression, including deconvolution to quantify immune cell populations. Additional analyses will include hierarchical clustering on principal components, differential gene expression, and pathway enrichment analysis, all of which may stratify patients who benefit and those who do not benefit from tebentafusp therapy.

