9.2.3 Peripheral Blood Analysis for ctDNA

ctDNA will be extracted from plasma and DNA isolated from plasma will be quantified and sequenced. Baseline quantity of ctDNA and the change in ctDNA across time will be correlated with clinical endpoints.

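### Kappa is a poor summary of ctDNA–tissue fusion concordance when nearly every tumour is expected to carry the fusion; report the ctDNA detection rate among tissue-positive patients instead

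*Protocol*

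**What the plan says.** The protocol's section 13.5 (Exploratory Analyses, peripheral blood ctDNA) sets out two uses of the fusion.

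- **Concordance.** "The concordance of detected fusion sequences in ctDNA and tissue will be assessed using cross-tabulation and kappa statistics".
- **Time course and outcome.** "The time course of the abundance of the *EWSR1::ATF1* fusion in ctDNA" is to be described, grouped by trend and, if events allow, related to response, clinical benefit, PFS and OS. The section calls this work exploratory and hypothesis-generating.

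Three other places bear on what the concordance table will look like.

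- Section 2.3 carries the heading "CCS is Characterized by an EWS-ATF1 Fusion and Expression of Melanocytic Antigens". Its text says a 1991 report "identified a balanced translocation between chromosomes 12 and 22 in select cases of CCS".
- Section 3.1.2 requires "Histologically confirmed diagnosis of HMB-45+ clear cell sarcoma which is unresectable and/or metastatic". It does not ask for a fusion test.
- The synopsis sets the size of the treated group: "23 patients will be on treatment arm".

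Section 9.2.3 describes the plasma assay more broadly and names no fusion: "ctDNA will be extracted from plasma and DNA isolated from plasma will be quantified and sequenced".

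**The concern.** Kappa compares observed agreement with the agreement expected by chance from the two margins. It is informative only when both methods yield a reasonable mix of positives and negatives. If the fusion characterises the disease, the tissue margin will be close to all-positive, and chance-expected agreement then rises to meet observed agreement. A sensitive ctDNA assay and an insensitive one could both return a kappa of zero. A reader who takes that at face value would conclude that plasma does not agree with tissue. A change of one patient in tissue status could also move kappa far more than any difference in the assay would.

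The question the investigators need answered is how often plasma detects a fusion that the tumour is known to carry, and kappa does not answer it.

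**Working it through.** **Inputs.** n = 23 is the planned treated group (synopsis). Tissue positivity is not given in the protocol. It is assumed to be 100%, then varied down to 18 of 23 (78%). The ctDNA counts are illustrations. One tissue–plasma pair per patient is assumed. The protocol states no figure for concordance, so there is none to reproduce.

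**Formula.** Let a = both positive, b = tissue-positive and ctDNA-negative, c = tissue-negative and ctDNA-positive, d = both negative.

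- Observed agreement: po = (a + d)/n
- Expected agreement: pe = [(a + b)(a + c) + (c + d)(b + d)]/n²
- Kappa = (po − pe)/(1 − pe)

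**Case 1: every tissue positive.** Then c = d = 0 and a + b = n. Observed agreement is po = a/n. Expected agreement is pe = n·a/n² = a/n. The two are equal, so kappa = 0 for every a below n. At a = n both are 1 and kappa is 0/0, which is undefined.

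| ctDNA-positive of 23 | Observed agreement | Expected agreement | Kappa |
|---|---|---|---|
| 12 | 52.2% | 52.2% | 0 |
| 20 | 87.0% | 87.0% | 0 |
| 22 | 95.7% | 95.7% | 0 |
| 23 | 100% | 100% | undefined |

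**Case 2: one tissue-negative patient.** Take a = 20, b = 2, c = 0, d = 1.

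- po = 21/23 = 0.913
- pe = (22 × 20 + 1 × 3)/529 = 443/529 = 0.837
- Kappa = (0.913 − 0.837)/(1 − 0.837) = 0.465, from unrounded values

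**Case 3: agreement held at 21/23 = 91.3%, number of tissue-negatives varied.** In each row ctDNA misses two tissue-positive patients and there are no false positives (b = 2, c = 0).

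| Tissue-negative | Kappa | ctDNA detection among tissue-positive |
|---|---|---|
| 0 | 0 | 21/23 = 91.3% |
| 1 | 0.465 | 20/22 = 90.9% |
| 2 | 0.623 | 19/21 = 90.5% |
| 3 | 0.701 | 18/20 = 90.0% |
| 5 | 0.777 | 16/18 = 88.9% |

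Overall agreement is the same in every row and the detection rate falls by 2.4 percentage points. Kappa runs from 0 to 0.78.

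**The alternative summary.** For 20 detected of 23 tissue-positive patients, the rate is 20/23 = 87.0%. The exact (Clopper–Pearson) 95% limits are the 2.5% quantile of Beta(20, 4) and the 97.5% quantile of Beta(21, 3), which are 66.4% and 97.2%. Where kappa is 0 for both 12/23 and 22/23, this measure gives 52% and 96%.

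**The case against.** **The tissue margin may not be constant.** Section 13.5 compares detected sequences, which is an assay result and not the biology. Section 9.1 plans biopsies at baseline and week 6 where feasible, and an on-treatment core may hold little tumour. Some tissue-negative results are therefore possible, and kappa would then be computable. This stands, but it does not rescue kappa: with a few tissue-negatives the value depends mainly on how many there are (case 3).

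**The cross-tabulation already shows the detection rate.** This stands, and it limits the harm. A careful reader of the table would not be misled.

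Some stronger readings are tempting but are not supported by the documents.

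- A reader might infer that fusion-negative tumours enter the concordance table as false ctDNA-negatives. They do not. A patient negative on both counts falls in the concordant-negative cell and raises kappa.
- A reader might infer that the outcome models will include patients whose tumour could never shed the fusion. Section 13.5 states no population for those models, and assessability for a correlative assay is commonly left to an analysis plan.
- A reader might infer that the whole ctDNA programme depends on this fusion. Section 9.2.3 plans quantification and sequencing without naming one.
- The reference in section 2.3 to select cases describes an early cytogenetic report. It does not estimate how many tumours lack the fusion.

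**Conclusion.** The point holds as an improvement to a stated method. If tissue is positive throughout, kappa is 0 at any imperfect agreement and undefined at perfect agreement. If one to five of 23 tissues are negative, kappa ranges from 0.47 to 0.78 at an unchanged 91% agreement. It therefore tracks the number of tissue-negatives more than the assay.

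This rests on near-universal tissue positivity, which section 2.3 suggests but does not quantify, and on a positive/negative table with one pair per patient.

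On the abundance analyses only a narrow point survives. A tumour shown to lack EWSR1::ATF1 would give a zero reading for that fusion whatever its burden, so zero should not be read as ctDNA-negative for that patient. How many such patients to expect cannot be known from the document.

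The weight is low. The work is exploratory, and no primary or secondary objective is touched.

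**What to change.** In section 13.5, keep the cross-tabulation and replace kappa with the ctDNA detection rate among tissue-fusion-positive patients (positive percent agreement) and its exact 95% confidence interval.

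As a minor addition, for the EWSR1::ATF1 abundance trend and outcome analyses only, state that patients whose tissue is shown to lack that fusion are not assessable, and report their number separately.

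The change costs a few words. Tissue fusion status is already needed for the planned concordance table, so no extra sample or visit follows. The protocol should say where that status comes from. Section 9.2.2 plans RNA sequencing ("Tumor cores will be analyzed by RNA sequencing") but lists expression analyses and does not mention fusion calling, so that step would need naming if it is the source. The only loss is possibly a few patients from the exploratory abundance models.

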13.5 Reporting and Exclusions

13.4.1 Evaluation of adverse events.

All patients who received at least one dose of protocol treatment will be accessible for adverse events. The NCI CTCAE version 5 will be used to determine the type and severity of the AEs. The observed adverse events, regardless of attribution, will be summarized for the treatment arm by the maximum grade observed for a patient of a particular AE.

13.4.2 Evaluation of response.

The primary analysis will be a modified intent to treat. It will include all patients who did not withdraw prior to initiating treatments. A per-protocol analysis will be done as a sensitivity analysis. Patient will be included in the ORR analysis if they had measurable disease and a baseline tumor assessment. If a patient did not have a follow-up tumor assessment, they will be classified as a non-responder.

APPENDIX A**Performance Status Criteria**

ECOG Performance Status Scale		Karnofsky Performance Scale	
Grade	Descriptions	Percent	Description
0	Normal activity. Fully active, able to carry on all pre-disease performance without restriction.	100	Normal, no complaints, no evidence of disease.
		90	Able to carry on normal activity; minor signs or symptoms of disease.
1	Symptoms, but ambulatory. Restricted in physically strenuous activity, but ambulatory and able to carry out work of a light or sedentary nature (e.g., light housework, office work)	80	Normal activity with effort; some signs or symptoms of disease.
		70	Cares for self, unable to carry on normal activity or to do active work.
2	In bed <50% of the time. Ambulatory and capable of all self-care, but unable to carry out any work activities. Up and about more than 50% of waking hours.	60	Requires occasional assistance, but is able to care for most of his/her needs.
		50	Requires considerable assistance and frequent medical care.
3	In bed >50% of the time. Capable of only limited self-care, confined in bed or chair more than 50% of waking hours.	40	Disabled, requires special care and assistance.
		30	Severely disabled, hospitalization indicated. Death not imminent.
4	100% bedridden. Completely disabled. Cannot carry on any self-care. Totally confined to bed or chair	20	Very sick, hospitalization indicated. Death not imminent.
		10	Moribund, fatal processes progressing rapidly.
5	Dead.	0	Dead.

APPENDIX B

Tebentafusp Toxicity Management Guidelines

Tebentafusp Toxicity Management Guidelines	
Worst Toxicity	Recommended Dose Modifications
Pruritus (graded per CTCAE v5.0)	
Grade 1	Continue dosing. If symptomatic, consider a systemic antihistamine regimen (see Grade 2 guidance below).
Grade 2	
May continue dosing. Intrapatient escalation is contraindicated if symptoms have not improved to Grade ≤ 1 prior to dosing. Treat according to institutional practice and/or implement the guidance described below. Use systemic management and/or local skin management as indicated by symptoms. With bullous formation or blistering rashes consider a dermatology consultation to rule out other causes (eg, bullous pemphigoid). Oral or topical corticosteroids can be used. If bullous formation or blistering recur, consult the Medical Monitor for guidance.
 
Antipruritic regimen:
 
A systemic antihistamine regimen is recommended as first-line management of pruritus, eg, nonsedating, long-acting antihistamine (cetirizine, 10 mg oral or equivalent). If a sedating antihistamine is preferred (eg, evening dosing), consider diphenhydramine 25 mg oral or intravenous (IV). The use of sedating antihistamines should be minimized in participants with comorbid pulmonary pathology including pulmonary metastases or underlying inflammatory airways disease such as chronic obstructive pulmonary disease or asthma.
 
Topical corticosteroid regimens
 
Preparation of recommended regimens is as follows:
 
 For the face and/or intertriginous areas (including genitalia), alclometasone 0.05% or hydrocortisone 2.5% creams are recommended. For other body areas (ie, the trunk and extremities), clobetasol or betamethasone 0.05% creams are recommended. Consider a spray preparation for ease of application on the trunk. For scalp involvement, consider a foam preparation. 
NOTE: Montelukast (10 mg orally) may be considered as an adjunctive therapy in participants with persistent symptoms despite antihistamine and topical corticosteroid therapy.
 
Prophylaxis for subsequent doses is generally not required after Grade 2 pruritus, but a nonsedating antihistamine may be considered, especially for recurrent or persistent symptoms.

Grade 3	
Hold all doses of tebentafusp until returned to CTCAE Grade ≤ 1.
 
 If Grade 3 pruritus resolves to \leq Grade 1 in < 7 days, 
 If at 20 or 30 mcg dose, stay at this dose level. Resume escalation once the current dose level is tolerated. If at 68 mcg, treatment may continue at the current dose level. If Grade 3 pruritus resolves to \leq Grade 1 in 7 to 21 days,

	
 ○ If at 20 or 30 mcg dose, stay at this dose level. Resume escalation once the current dose level is tolerated ○ If at 68 mcg, treatment may restart at the current dose level ○ Mandatory corticosteroid prophylaxis is required for at least the next 3 doses. • If Grade 3 rash/pruritus does not resolve within 21 days, permanently discontinue all study interventions. 
Manage pruritus according to the institutional protocol and guidance below.
 
Management:
 
Treat according to institutional practice, which generally includes an antipruritic regimen (see Grade 2 management above). In addition, corticosteroid treatment (systemic) can be considered for pruritus that does not respond to antihistamine, topical corticosteroid, or montelukast therapy (recommend oral prednisone 20–40 mg, a single dose of 125 mg hydrocortisone IV, or the equivalent for refractory pruritus). For recommended systemic or topical regimens, refer to Grade 2 management above.
 
Prophylaxis:
 
In participants experiencing Grade 3 pruritus, administration of a nonsedating antihistamine prophylaxis dose is recommended for the subsequent dose of tebentafusp, approximately 1–2 hours prior to the tebentafusp dose being administered (eg, cetirizine 10 mg or equivalent).
 
Prophylaxis with corticosteroid should be considered if pruritus recurs at a similar or worse severity despite antihistamine prophylaxis and is required if the initial episode does not resolve in < 7 days (recommend oral prednisone 20–40 mg, a single dose of 125 mg hydrocortisone IV, or the equivalent). If steroid prophylaxis is used, the steroid dose should be titrated to the minimum effective dose and ultimately discontinued if possible.

Grade 4	
Permanently discontinue tebentafusp
 
As above for Grade 3 except administer intravenous corticosteroid (eg, 2 mg/kg methylprednisolone or equivalent); additionally, consultation with a dermatologist is recommended.

Rash/Photosensitivity (graded per CTCAE v5.0)	
Grade 1	Continue dosing. If symptomatic, consider a systemic antihistamine regimen according to management guidance for pruritus (above).
Grade 2	
Hold all doses of tebentafusp until improvement to CTCAE Grade ≤ 1.
 
 • If at 20 or 30 mcg dose, may escalate to next dose level. • If at 68 mcg, continue at this dose level 
Treat according to institutional practice and/or implement guidance below.
 
Use systemic management and/or local skin management as indicated by symptoms. With bullous formation or blistering rashes, consider a dermatology consultation to rule out other causes (eg, bullous pemphigoid). Oral or topical corticosteroids can be used for bullous formations or blistering. If bullous formation or blistering recur, consult the Medical Monitor for guidance.

	
Antipruritic regimen:
 
A systemic antihistamine regimen is recommended as first-line management of pruritus, eg, nonsedating, long-acting antihistamine (cetirizine, 10 mg oral or equivalent). If a sedating antihistamine is preferred (eg, evening dosing) consider diphenhydramine 25 mg oral or IV. The use of sedating antihistamines should be minimized in participants with comorbid pulmonary pathology including pulmonary metastases or underlying inflammatory airway disease such as chronic obstructive pulmonary disease or asthma.
 
Topical corticosteroid regimens
 
Preparation of recommended regimens is as follows:
 
 For the face and/or intertriginous areas (including genitalia), alclometasone 0.05% or hydrocortisone 2.5% creams are recommended. For other body areas (ie, the trunk and extremities), clobetasol or betamethasone 0.05% creams are recommended. Consider a spray preparation for ease of application on the trunk. For scalp involvement, consider a foam preparation. 
NOTE: Montelukast (10 mg orally) may be considered as an adjunctive therapy in participants with persistent symptoms despite antihistamine and topical corticosteroid therapy.
 
Prophylaxis for subsequent doses is generally not required after Grade 2 rash, but a nonsedating antihistamine may be considered, especially for recurrent or persistent symptoms.
 
Consider performing a skin punch biopsy (Section 8.7.2) and/or photographing the affected area (Note: include a reference measurement scale, such as a ruler, in the photograph whenever possible).

Grade 3	
Hold all doses of tebentafusp until improvement to CTCAE Grade \leq 1.
 
 If Grade 3 rash resolves to \leq Grade 1 in < 7 days, 
 If at 20 or 30 mcg dose, stay at this dose level. Resume escalation once the current dose level is tolerated. If at 68 mcg, treatment may continue at the current dose level. If Grade 3 rash resolves to \leq Grade 1 in 7 to 21 days, 
 If at 20 or 30 mcg dose, stay at this dose level. Resume escalation once the current dose level is tolerated. If at 68 mcg, treatment may continue at the current dose level. Corticosteroid prophylaxis is required for at least the next 3 doses If Grade 3 rash does not resolve within 21 days, permanently discontinue all study interventions. 
Manage rash according to the institutional protocol and guidance below.
 
Management:
 
Treat according to institutional practice, which generally includes an antipruritic regimen (see Grade 2 management above). In addition, corticosteroid treatment (systemic) can be considered for symptomatic rash that does not respond to antihistamine, topical corticosteroid, or montelukast therapy (recommend oral prednisone 20–40 mg, a single dose of 125 mg hydrocortisone intravenous, or the equivalent for refractory rash). For recommended systemic or topical regimens, refer to Grade 2 management above.
 
Prophylaxis:

	
In participants experiencing Grade 3 rash, administration of a nonsedating antihistamine prophylaxis dose is recommended for the subsequent dose of tebentafusp, approximately 1–2 hours prior to the tebentafusp dose being administered (eg, cetirizine 10 mg or equivalent).
 
Prophylaxis with corticosteroid should be considered if rash recurs at a similar or worse severity despite antihistamine prophylaxis and is required if any episode does not resolve in < 7 days (recommend oral prednisone 20–40 mg, a single dose of 125 mg hydrocortisone intravenous, or the equivalent). If steroid prophylaxis is used, the steroid dose should be titrated to the minimum effective dose and ultimately discontinued if possible.

Grade 4	
Permanently discontinue tebentafusp.
 
As above for Grade 3 except administer intravenous corticosteroid (eg, 2 mg/kg methylprednisolone or equivalent); additionally, consultation with a dermatologist is recommended.

Infusion-Related Reactions/Anaphylaxis (events during infusion; graded per CTCAE v5.0)	
Any grade	Acute reactions occurring while study treatments are infused should be treated as needed using institutional guidelines. In the event of anaphylactic/anaphylactoid reactions, any therapy necessary to restore normal cardiopulmonary status should be implemented immediately.
Grade 1	Administer medications for symptomatic relief as needed. Infusion interruption may be considered until resolution of the event (up to 4 hours). The infusion rate of the study interventions may be decreased by 50%. If resolved with a decreased rate of infusion, any subsequent infusions can be administered at the reduced rate.
Grade 2	
Stop tebentafusp infusion and keep the IV line open. Treat according to institutional practice. Provide all supportive measures as indicated. Provide supplemental oxygen and fluids, as needed.
 
 Monitor vital signs (eg, BP, pulse rate, respiration rate, temperature, and oxygen saturation) until resolution. Administer medications for symptomatic relief as needed. Antihistamines, acetaminophen (paracetamol), or corticosteroids may be administered, as needed, at the discretion of the Investigator. Restart infusion only once the infusion reaction resolves (within 4 hours of the initial start of infusion), ensuring there is a minimum observation period of one hour from stop of initial infusion to restart at the reduced rate. Administer oral premedication (eg, 1000 mg of acetaminophen/paracetamol, 50–100 mg diphenhydramine hydrochloride, or alternative antihistamine) 60 minutes prior to restarting the infusion, accounting for prior doses/time given for management of the initial reaction. Restart the infusion at 50% of the previous rate under continuous observation. If the AE recurs at the reinitiated slow rate of infusion, and despite oral premedication, then permanently discontinue the participant from study treatment.
Grade 3 or 4	
Discontinue tebentafusp infusion immediately and permanently discontinue participant from study treatment.
 
NOTE: Grade 3 infusion-related reactions that improve by at least 1 grade within 6 hours of onset will not require permanent discontinuation. If treatment is continued, all guidance provided for the management of Grade 2 reactions must be followed.
 
Manage severe infusion-related reactions per institutional standards. Provide supplemental oxygen, fluids, and other resuscitative measures as needed. Monitor vital signs (eg, BP, pulse rate, respiration rate, temperature, and oxygen saturation) until resolution.

Infusion-Related Reactions/Cytokine Release Syndrome (occurring after infusion/injection; graded per ASTCT 2019, see Table 6)	

Grade 1	
 Admit for inpatient monitoring (unless already hospitalized per protocol). Assess for potential infection and treat fever and neutropenia. Manage according to individual symptoms. Treat symptomatically as indicated, including antihistamines, antipyretics, antiemetics, and/or analgesics as needed. Initiate bolus and/or maintenance IV fluids and carefully monitor fluid balance. Vigilantly monitor for escalation to Grade 2 CRS with frequent vital signs monitoring (eg, assess vital signs every 2 hours) Strongly consider early, high dose corticosteroid therapy if there is progressive worsening of vital signs (see Grade 2 below). Consider prophylactic electrolyte supplementation for participants receiving IV fluids with low-normal serum electrolyte levels. 
Once symptoms resolve, at the next dose, do the following:
 
 If at 20 or 30 mcg dose, may escalate to next dose level. If at 68 mcg, continue at this dose level
Grade 2	
 Increase monitoring with continuous cardiac and pulse oximetry monitoring and continue or increase vital signs monitoring (eg, assess vital signs every hour). To manage hypotension, administer bolus IV fluids (recommended rate of approximately 1 L per hour) and supplemental oxygen for hypoxia or respiratory distress. If not rapidly resolved (ie, within 2-3 hours of onset) with fluids and/or supplemental oxygen, administer high dose IV corticosteroid therapy (eg, methylprednisolone 1 to 2 mg/kg initial dose or equivalent) and/or tocilizumab 8 mg/kg IV (not to exceed 800 mg/infusion) per institutional guidelines until symptoms (eg, hypotension) resolve. Consider prophylactic electrolyte supplementation for participants receiving IV fluids with low-normal serum electrolyte levels. Consider additional respiratory support as needed to manage ongoing or persistent respiratory distress. 
Once symptoms resolve, at the next dose, do the following:
 
 Administer corticosteroid premedication (eg, dexamethasone 4 to 12 mg or equivalent) at least 30 minutes prior to the next dose If at 20 or 30 mcg dose, may escalate to next dose level. If at 68 mcg, continue at this dose level; monitor for at least 16 hours post-dose
Grade 3	
Management as above (Grade 2) and include the following measures:
 
 Escalate level of care (eg, intensive care unit) as clinically indicated. Maximize immunosuppression with continued high dose IV corticosteroid (eg, methylprednisolone 2 mg/kg/day or equivalent) and/or tocilizumab 8 mg/kg IV (not to exceed 800 mg/infusion) per institutional guidelines. For persistent hypotension, treat with a single vasopressor (with or without vasopressin). 
 Consider adding further immunosuppression measures or additional interventions according to the institutional cytokine release protocol (eg, administer or repeat tocilizumab if not already implemented). Continue to manage symptoms and vigilantly monitor for escalation. For any Grade 3 CRS, restart tebentafusp only after discussion and written approval from the Medical Monitor. 
Once symptoms resolve, at the next dose, do the following:
 
 Administer corticosteroid premedication (eg, dexamethasone 4 to 12 mg or equivalent) at least 30 minutes prior to the next dose If at 20 or 30 mcg dose, stay at this dose level. Resume escalation once the current dose level is tolerated. If at 68 mcg, continue at this dose level; monitor for at least 16 hours post-dose

Grade 4	
Management as above (Grade 3) and include the following measures.
 
 For persistent hypotension, treat with multiple vasopressors (with or without vasopressin). For persistent hypoxia, provide supplemental oxygen using a positive-pressure device. If appropriate, consider additional measures according to the institutional cytokine release protocol. 
Permanently discontinue tebentafusp.

Elevated Liver Enzymes (graded per CTCAE v5.0)	
Grade 2	
 Institute regular monitoring of liver enzymes until improving or resolved. Evaluate concurrent medications for agents that may prolong or exacerbate elevated liver enzymes. Consider IV corticosteroid therapy (eg, methylprednisolone 0.5 to 1 mg/kg/day or the equivalent) if not improving within 72 hours.
Grade 3 or 4	
Hold all doses of tebentafusp until returned to CTCAE Grade ≤ 1.
 
 Institute regular monitoring of liver enzymes until improving or resolved. Administer intravenous steroids (eg, methylprednisolone 0.5 to 1 mg/kg/day or the equivalent) if no improvement within 24 hours. Consider abdominal imaging and a hepatology consult for persistent elevated liver enzymes, onset of clinical signs or symptoms of liver dysfunction (eg, abdominal pain, nausea, vomiting, jaundice), or impact on liver synthetic function. For any Grade 3 elevated liver enzyme elevation, restart tebentafusp only after discussion and written approval from the Medical Monitor. 
Once elevated liver enzymes improve to NCI CTCAE Grade ≤ 1, if restarting tebentafusp, resume treatment as follows:
 
 If elevated liver enzymes occurred in the setting of Grade 3 CRS, resume at the current dose level. Resume escalation once the current dose level is tolerated. If elevated liver enzymes occurred outside the setting of Grade 3 CRS, then resume intrapatient escalation if the current dose level is less than 68 mcg; otherwise, resume treatment at the current dose level if intrapatient escalation has been completed.
Vomiting (graded per CTCAE v5.0)	
Grade 2	
 Administer antiemetic therapy as per institutional standard. Provide IV fluid support and other supportive measures for additional AEs as needed.
Grade 3 or 4	
 Consider holding all doses of tebentafusp until improvement to NCI CTCAE Grade ≤ 1. Administer antiemetic therapy as per institutional standard. Provide IV fluid support and other supportive measures for additional AEs. Consider instituting antiemetic premedication for at least the next dose (eg, ondansetron 8 mg PO/IV or equivalent).
Other Clinically Significant Adverse Events (graded per CTCAE v5.0)	
Treat according to institutional practice and for potential immune-related AEs of Grade ≥ 3 ; treatment with corticosteroids should be considered. Consult the Medical Monitor for further guidance as needed.	
Grade 3 or 4	
Study medication(s) should be permanently discontinued unless AEs improves to Grade 1 or 0, the Investigator believes the overall benefit-risk favors continued treatment, and there is agreement with the Medical Monitor that the participant may restart treatment at the current or reduced dose.

Confidential
